8. STATISTICS AND ANALYSIS

8.1. Description of Statistical Methods

The efficacy of Sleepio will be assessed by comparing the SCI scores of the intervention and control groups from baseline to immediately post-intervention, following an intention to treat analysis approach. Changes in the primary outcome measure from baseline to post-intervention will be assessed with analysis of variance (ANOVA) (or linear mixed model or non-parametric equivalents if necessary) with inclusion of baseline score as a covariate.

Secondary outcomes will be assessed with ANOVA (or linear mixed model or non-parametric equivalents if necessary). EQ-5D-5L responses will be converted into utility values using population preferences (van Hout et al., 2012) and combined with survival information to calculate Quality Adjusted Life-Years (QALYs). All resource use will be valued using 2018/19 unit costs obtained from healthcare compendiums, (Curtis and Burns 2018) NHS reference costs, (<https://improvement.nhs.uk/resources/reference-costs/>) and British National Formulary (<https://www.bnf.org/>). Costs of CBT-I will be obtained from the trial.

An incremental analysis will be performed, assessing the differences in costs between the two interventions and dividing by the difference in QALYs gained in order to generate an incremental cost-effectiveness ratio (ICER). ICERs will be estimated using an NHS perspective. The 10 000 bootstrapped pairs of incremental costs and incremental QALYs will be plotted on cost-effectiveness planes to display the uncertainty in the estimated ICER. Cost-effectiveness acceptability curves (CEACs) will be derived to display the probability of the CBT treatment being cost-effective, as the ceiling ratio for the maximum acceptable cost-effectiveness ratio varies from £0 to £85 000 per QALY gained.

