1. SYNOPSIS

Long Study Title	An Investigation into the Efficacy of Online Cognitive Behaviour Therapy for Insomnia (“Sleepio”) for Stroke Survivors	
Short Study Title (to be used on participant-facing documents, if applicable)	Improving sleep in rehabilitation after stroke (INSPIRES)	
Nature of Study Participants	Stroke survivors	
Intended number of participants	86	
Design	Randomised controlled	
Location	In the participant's home / online	
	Objectives	Outcome Measures
Primary	The primary objective of this study is to assess whether self-reported sleep quality in stroke survivors is improved following online Cognitive Behavioural Therapy for Insomnia (“Sleepio” programme).	The primary outcome measures for this study will be the change in Sleep Condition Indicator score following completion of the programme.
Secondary	
The secondary objectives are to assess changes in measures of sleep quality and self-reported measures of quality of life and anxiety following the intervention and at 8 week follow up.
 
To assess the cost-effectiveness of online CBT-I in stroke survivors when compared to a brochure of sleep hygiene information.
	
Changes in sleep fragmentation and wake after sleep onset, assessed with actigraphy, sleep onset latency assessed through the sleep diaries, anxiety and depression using the PHQ9 and GAD7, quality of life using the Stroke impact scale-8 and Euroqol-5 Dimensions- 5 Levels (EQ-5D-5L)
 
Changes in healthcare costs during the 8-week follow up.

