5.5. Baseline Assessments

After the signed consent form has been received by the researchers, the participant will be sent the GAD-7, PHQ-9, SCI, Stroke Impact Scale-8, Stroke Efficacy questionnaire and EQ-5D-5L to complete. Participants will also receive a questionnaire asking them to recall over the last 8 weeks all the contacts they have had with the healthcare service. This will be a modified version of the Client Service Receipt Inventory (CSRI).

We will also ask them to wear an actigraphy monitor on their wrist for one week and to complete a sleep diary at the same time. We will provide them with a prepaid envelope to send the materials back.

We will also record demographic variables including; age, sex, partner status, whether they share a bed, medications, employment status and date of stroke.

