5.6. Subsequent Assessments

Participants randomised to the intervention group will receive access, via web link and activation code to the digital CBT-I programme “Sleepio”. This programme will require the participant to keep a daily sleep diary and engage in weekly sessions comprising weekly CBT-I content. Participants randomised to the control group will be given access to an online sleep diary to complete for one week. They will also receive a brochure with sleep hygiene information and then will be asked to complete the online sleep diary again 8 weeks later.

During the trial, participants will be asked to keep a record, in a specially designed log book, of their contacts with the healthcare service.

Upon completion of the programme, participants will once again be sent questionnaires to complete (PHQ-9, GAD-7, SIS-8, Stroke Efficacy questionnaire and EQ-5D-5L), in addition to the wrist worn actigraphy monitor and the sleep diary to use for one week.

At 8 weeks follow up, all assessments conducted as baseline will be repeated and the intervention group will complete a debriefing feedback questionnaire.

6. Feasibility and Adverse events

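### The Sleep Condition Indicator (SCI) is collected at the 8-week follow-up, but its change at that visit is not a named outcome and has no planned comparison

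*Combined protocol and SAP*

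**What the plan says.** **Primary outcome.** The synopsis defines it as the "change in Sleep Condition Indicator score following completion of the programme". Section 8.1 ties the analysis to the same window, "comparing the SCI scores of the intervention and control groups from baseline to immediately post-intervention", with baseline score as a covariate.

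**Secondary objective.** The synopsis states: "The secondary objectives are to assess changes in measures of sleep quality", together with quality of life and anxiety, both after the intervention and at the 8-week follow-up.

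**Secondary outcomes.** The list beside that objective is itemised. Its sleep entries are "Changes in sleep fragmentation and wake after sleep onset, assessed with actigraphy, sleep onset latency assessed through the sleep diaries". PHQ-9, GAD-7, the Stroke Impact Scale-8, EQ-5D-5L and healthcare costs follow. SCI is not listed. Section 8.1 gives a generic method for secondary outcomes and no time point.

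**Collection.** At baseline (section 5.5), "the participant will be sent the GAD-7, PHQ-9, SCI, Stroke Impact Scale-8, Stroke Efficacy questionnaire and EQ-5D-5L to complete". Section 5.6 adds: "At 8 weeks follow up, all assessments conducted as baseline will be repeated". SCI is therefore collected at 8 weeks. The post-intervention set in section 5.6 is given as "PHQ-9, GAD-7, SIS-8, Stroke Efficacy questionnaire and EQ-5D-5L", without SCI.

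**Control access.** Sections 3, 5.4 and 8.3 give control participants Sleepio only after the 8-week follow-up.

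**The concern.** The protocol sets itself the question of sleep quality at 8 weeks and collects its main self-reported sleep scale at that visit. It then leaves that scale out of both the outcome list and the analysis. Followed as written, the 8-week sleep question is answered by two actigraphy variables and one diary variable, none of which is the scale on which efficacy will be claimed. An SCI effect that fades by follow-up and one that lasts would give the same planned SCI result.

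The risk is selective reporting. If the 8-week SCI analysis is added once the data are in hand, a reader cannot tell whether it would have been reported had it been unfavourable. A sound result would be discounted for the same reason.

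**Working it through.** **Step 1: trace SCI through the document.**

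| Visit | Collected? | Named outcome? | Planned comparison? |
|---|---|---|---|
| Baseline | Yes (5.5) | n/a | Covariate (8.1); minimisation factor (3, 5.4) |
| Post-intervention | Required by the synopsis and 8.1; missing from the list in 5.6 | Yes, primary | Yes (8.1) |
| 8-week follow-up | Yes (5.5 with 5.6) | Not named | None stated |

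The last row is the gap. The middle row holds a second inconsistency: the post-intervention list omits the primary instrument at the primary time point.

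**Step 2: is the 8-week contrast a valid randomised one?** Yes. Controls have no access to Sleepio through the trial until that follow-up is complete.

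**Step 3: reproduce the plan's sample size.** Inputs from section 8.2: d = 0.7, alpha 0.05, power 80%, 1:1 allocation, 68 datasets. Sidedness is not stated.

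- Normal approximation, two-sided: n per arm = 2(1.960 + 0.842)² / 0.7² = 2 × 7.85 / 0.49 = 32.04, rounded up to 33, total 66.
- t-test, two-sided: 33.02 per arm, rounded up to 34, total 68. This matches the plan.
- One-sided (normal approximation): total 52. The calculation is therefore two-sided.

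**Step 4: what an 8-week SCI comparison could show at the same N.** The documents give no 8-week effect, so d is an assumption and a range is shown. Power is for an unadjusted two-sided t-test at 0.05 and ignores any gain from baseline adjustment. The 34 per arm is 68 / 2. The 32 per arm is 86 × 0.75 = 64.5, halved and rounded down.

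| Assumed d at 8 weeks | 34 per arm | 32 per arm |
|---|---|---|
| 0.7 | 81% | 79% |
| 0.6 | 68% | 66% |
| 0.5 | 53% | 50% |
| 0.4 | 37% | 35% |

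The effect detectable with 80% power is d = 0.69 (34 per arm) or 0.71 (32 per arm).

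**Step 5: precision.** With 34 per arm, the standard error of the difference in SD units is about √(2/34) = 0.243, so the 95% interval is about ±1.96 × 0.243 = ±0.48. An observed d of 0.4 would give roughly −0.08 to 0.88. That interval contains both zero and the 0.7 planned for the primary, so non-significance alone would not show that the effect had been lost.

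**Step 6: what do the 8 weeks run from?** Sections 3 and 5.6 have controls repeat the diary 8 weeks after the diary and brochure stage, whereas the intervention is a six-week programme. Counted from the start of the programme, follow-up falls about 8 − 6 = 2 weeks after its end. Counted from completion, it falls 8 weeks after. The text does not settle which applies, and the meaning of a persistence result depends on it.

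**The case against.** The strongest reply is that the secondary objective already covers SCI. It speaks of measures of sleep quality at 8 weeks, and section 3 describes SCI as self-reported sleep quality. Section 8.1 has a generic method for secondary outcomes and allows a linear mixed model. On that reading, only the wording of a list is at fault.

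Much of this stands. A reader might infer that 8-week SCI has no place in the trial's aims, or that the trial cannot say whether its effect lasts. The documents support neither inference: the objective can be read to include SCI, the data are collected, and the randomised contrast is intact. What the reply does not do is supply a plan. An objective is not an outcome. The outcome list names specific instruments and leaves this one out. The mixed model appears only as a fallback, and for SCI it sits in a sentence limited to baseline to post-intervention.

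Three further points stand in the plan's favour. A post-intervention primary time point is legitimate, and no primary inference, error rate or sample size changes. It would be tempting to size the problem as 68 unanalysed SCI scores, but a count of forms shows no bias or loss of power, and the voucher in section 8.3 is paid per time point and not per questionnaire. It would also be tempting to rest any claim of sustained benefit on this one comparison; Steps 4 and 5 show why a non-significant result could not bear that weight.

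A literal reading of the list in section 5.6 might suggest that SCI is not collected post-intervention at all. Section 3 says the questionnaires are sent again at that point, and the synopsis and section 8.1 depend on SCI there, so a drafting omission is the more likely explanation. It still needs correcting.

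**Conclusion.** The point holds as a gap in pre-specification. Persistence of the primary effect on SCI is not a named outcome and has no planned comparison, although the data will exist and a stated objective points towards them. This goes beyond missing detail, because an itemised list and a stated time window both leave the comparison out.

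The consequence is limited to how an 8-week SCI result can be used: as written, it would be open to the charge of being post hoc. The primary analysis is untouched. The power figures assume a two-sided unadjusted t-test and an 8-week effect that the documents do not give. On those terms the comparison is about as well powered as the primary if d stays at 0.7, and close to even odds if it falls to 0.5.

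**What to change.** - **Synopsis:** name change in SCI from baseline to the 8-week follow-up as a secondary outcome.
- **Section 8.1:** analyse it with the same baseline-adjusted between-group comparison as the primary, or with one mixed model holding both post-baseline visits. State which. Keep the primary test at post-intervention.
- **Reporting:** give the 8-week estimate with its confidence interval, and say that a non-significant result will not be read as loss of effect.
- **Timing:** state what the 8 weeks run from, for both arms.
- **Section 5.6:** reconcile the post-intervention questionnaire list, which omits SCI, with the synopsis and section 8.1, which require it there.

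The cost is a few lines of wording and one further model (none if the mixed model is used for both visits). No new data, visits or participants are needed, and N does not change. The downside is one more secondary comparison, with modest power if the effect shrinks.

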8.2. The Number of Participants

68 full datasets (1:1 ratio intervention to control) are intended to be collected for this study. This is based on a power calculation using the between groups effect size estimate ($d=1.2$) from a previous study of digital CBT-I in people with insomnia (Espie et al., 2012). This would therefore require 24 participants in total to find an effect. However, we wish to also include people with sleep disturbance who do not meet the criteria for insomnia. Based on our open-label feasibility study for digital CBT-I in this population (Smejka et al., 2022) we anticipate that 50% of participants will not meet the criteria for insomnia, and based on that study we would anticipate a more modest effect size ($d=0.7$), which would require 68 participants (assuming $\alpha=0.05$ and power of 80%). Allowing for approximately 25% drop out, we therefore aim to recruit 86 participants in total. This should allow us to do a subgroup analysis including only people who meet the criteria for insomnia, as well as a full group analysis.

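### Section 8.1 states intention to treat, but its default ANOVA keeps only people with a post-intervention SCI, and no section says whether people who stop Sleepio early are sent one

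*Combined protocol and SAP*

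**What the plan says.** **Principle and method (Section 8.1).** Efficacy is judged by "comparing the SCI scores of the intervention and control groups from baseline to immediately post-intervention", "following an intention to treat analysis approach". The model is "analysis of variance (ANOVA) (or linear mixed model or non-parametric equivalents if necessary) with inclusion of baseline score as a covariate". The section does not say what would make an alternative necessary. Neither it nor any other section defines an analysis set, a method or assumption for missing outcomes, or a sensitivity analysis.

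**Expected loss (Section 8.2).** "68 full datasets (1:1 ratio intervention to control) are intended to be collected for this study". The target of 86 comes from "Allowing for approximately 25% drop out".

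**Collection of the outcome (Sections 3 and 5.6).** Section 5.6 states: "Upon completion of the programme, participants will once again be sent questionnaires to complete". The questionnaires it then lists are the PHQ-9, GAD-7, SIS-8, Stroke Efficacy questionnaire and EQ-5D-5L; the SCI is not among them. Section 3 gives each arm its own trigger for the pack: finishing the programme for Sleepio, and a sleep diary for controls. Neither section covers a participant who stops Sleepio part-way. Section 6.1 records reasons for withdrawal where known, but says nothing about follow-up afterwards.

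**The concern.** Intention to treat requires more than analysing people in their assigned arm. It also needs an attempt to obtain the outcome from everyone randomised, and a stated way of handling those for whom the attempt fails. This plan names the principle and specifies neither.

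The collection rule takes this beyond silence on imputation. Read literally, whether the primary outcome is requested in the Sleepio arm can depend on engagement with six weeks of sessions, while the control arm's trigger is a different and lighter one. If people who do badly on Sleepio stop and are then not assessed, the randomised comparison is distorted in favour of Sleepio. A positive result could not then be read safely as the effect of being offered the programme.

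**Working it through.** **1. The plan's own numbers.** Inputs from Section 8.2: d = 0.7, alpha 0.05, power 80%, 1:1 allocation, about 25% dropout. Sidedness is not stated; two-sided reproduces the figure.
- Two-sample t-test: 33.02 per arm, rounded up to 34, so 2 × 34 = 68. This matches the plan.
- Dropout: 34 × 1.25 = 42.5, rounded up to 43 per arm, so 86. This matches. Dividing instead gives 68 / 0.75 = 90.7, or 91.
- Loss implied by the plan's two totals: 86 − 68 = 18 people, and 18 / 86 = 20.9%.
- A true 25% loss from 86 would leave 64.5 people. Power at d = 0.7 would be about 79%, against about 81% with 68.

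So the plan expects to analyse roughly four in five of those randomised. The effect on power is small; the issue is who is missing.

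**2. Who enters the default model.** Write Y0 for baseline SCI and Y1 for post-intervention SCI. The model is Y1 = a + τ·arm + β·Y0 + error. A participant without Y1 has no row. A mixed model with Y0 as covariate and Y1 as the only outcome has one observation per person, so it excludes the same people. Two changes alter this:
- Adding the 8-week SCI as an outcome brings in people who missed Y1 but returned at 8 weeks. Section 5.6 already repeats all baseline assessments then, and Section 5.5 lists the SCI at baseline.
- Making Y0 an outcome as well keeps everyone with a baseline score in the model. That should be everyone randomised, because Section 5.4 minimises on baseline SCI.

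**3. Who is likely to lack Y1.** The sections side by side:
- Section 3, Sleepio: pack sent when the programme is finished. Early stoppers: not addressed.
- Section 3, control: pack sent after a diary described there as lasting six weeks, although the same section earlier gives controls one-week diaries.
- Section 5.6: a single trigger, programme completion, with no SCI in the list.
- Section 8.1: needs a post-intervention SCI from both arms.

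The two arms therefore have different triggers, and the Sleepio trigger is linked to adherence.

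**4. When the loss biases the estimate.** This is a simulation under stated assumptions: 43 per arm, SCI standardised to SD 1, baseline-to-follow-up correlation 0.5, true d = 0.70, 4,000 runs, ANCOVA on observed cases. In the second and third rows, the log-odds of being missing in the Sleepio arm are −1.3 − 1.0 × (the score named), and in the control arm a constant −1.3, which is 1 / (1 + e^1.3) = 21%.

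| Missingness depends on | Overall missing | Mean estimate of d |
|---|---|---|
| Nothing | 24.9% | 0.70 |
| Baseline SCI, in the Sleepio arm | 23.3% | 0.70 |
| Post-intervention SCI less the treatment effect, in the Sleepio arm | 23.3% | 0.87 |

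The last two rows have the same total loss, yet one is unbiased and the other overstates the effect by 0.87 − 0.70 = 0.17, or 24%. The dropout rate alone cannot show which case applies.

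**The case against.** The best defence is that the plan is terse, not wrong. Analysing observed participants in their assigned arms is compatible with Section 8.1, which also permits a mixed model. Both arms have a trigger in Section 3, and finishing the programme can be read as the end of a fixed six-week period. Section 8.3 pays a voucher per assessment time point and attaches no completion condition. The missing SCI in 5.6 looks like a listing slip, since Sections 1 and 8.1 both require it, and it affects both arms equally.

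Much of this is fair, and it rules out several stronger readings that a reader might infer:
- **That the ANOVA is restricted to full datasets.** That phrase is a collection target in Section 8.2; Section 8.1 imposes no such restriction.
- **That the result is a completer effect.** People are excluded for lacking the score, not for leaving Sleepio unfinished. A non-completer who returns the SCI stays in the assigned arm.
- **That the estimate must favour Sleepio.** It does so only if loss depends on the unseen outcome; the documents give no evidence either way.
- **That the effect among all randomised is about 0.75 × 0.70 = 0.53.** This assumes that 0.7 applies to completers only and that those lost gain nothing. Section 8.2 gives 0.7 as the effect expected in the mixed sample, without that limit.
- **That a quarter will lack the primary outcome.** The 25% is general dropout, and the plan's totals imply 21%.

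What the defence does not answer is that early stoppers have no stated follow-up, the fallback model has no trigger, and nothing says how a missing SCI is handled.

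**Conclusion.** The point holds as a gap between the stated principle and the specified method. The default analysis is available-case and, on the plan's own totals, would leave out about 18 of 86 people (21%), provided that those lost lack the post-intervention SCI. The collection rule, read literally, can make that loss depend on engagement in the Sleepio arm. Sections 5.6 and 8.1 also conflict on whether the SCI is collected at that visit.

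Bias is a risk, not a demonstrated result. The 0.87 against 0.70 rests on the assumed dropout model and correlation, and shows a plausible scale, not a forecast. If loss depends only on arm and baseline SCI, the planned analysis is unbiased. The primary conclusion is exposed enough, and the remedy cheap enough, that the plan should be changed: the dispatch rule as soon as possible, and the analysis before any unblinded look at outcomes.

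**What to change.** 1. **Sections 3 and 5.6.** Send the post-intervention pack, with the SCI listed, to every randomised participant at the same fixed time after randomisation in both arms, whether or not they finished the programme. This deals with the problem at source.
2. **Section 8.1.** Make the primary analysis a linear mixed model in assigned arms, with baseline, post-intervention and 8-week SCI as outcomes, a common baseline mean across arms, and the post-intervention arm contrast as primary. Multiple imputation using baseline and 8-week SCI is an acceptable alternative. Baseline should be an outcome: if it is only a covariate, people with neither follow-up score are still excluded.
3. **Section 8.1.** Add one sensitivity analysis that imputes missing Sleepio scores from the control arm. It is needed because the model in item 2 still assumes that missingness depends only on arm and observed scores.

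The cost is wording in three sections and modest extra analysis; no new assessment time point is needed. The estimate may be smaller than the available-case one.

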3. STUDY DESIGN

The study will be a single-blinded randomised controlled trial involving the completion of a six-week digital CBT-I programme. Following written informed consent, participants will be posted baseline questionnaires to complete and an actigraphy monitor to record objective sleep measures for one week. After this, participants will be randomised to CBT-I or control using an online randomisation software (rando.la) with minimisation of between group differences based on age and baseline self-reported sleep quality (Sleep Condition Indicator (SCI) score). The control group will be given access to an online sleep diary to complete daily for one week. They will also be given a brochure containing sleep hygiene information. 8 weeks later they will be asked to complete the online sleep diary again for one week.

Participants allocated to Sleepio will complete daily online sleep diaries for the duration of the study and will receive weekly online CBT-I sessions as part of the programme. Both groups will complete their programmes at home.

Participants will be sent the questionnaires and actigraphy monitor again to be worn for another week immediately following completion of the programme (Sleepio) or following the 6-week sleep diary (control) and at 8 weeks follow up. At 8 weeks follow up, participants in the intervention group will also be sent a debriefing questionnaire to get feedback on the programme and the research study.

Participants allocated to the control group will be sent a web link and activation code for the Sleepio programme following completion of the 8 week follow up.

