5.4. Randomisation

Participants will be randomised into the CBT-I or control group based using an online randomisation software (rando.la) with minimisation of between group differences based on baseline SCI score and age.

All participants randomised to the control group will be offered the opportunity to undergo the Sleepio programme after completion of the 8-week follow up.

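### Allocation is minimised on baseline SCI and age, but the primary model omits age and the secondary analyses name no baseline covariate; adding them is a free improvement

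*Combined protocol and SAP*

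**What the plan says.** Section 3 describes "minimisation of between group differences based on age and baseline self-reported sleep quality", and Section 5.4 repeats the same two factors: "minimisation of between group differences based on baseline SCI score and age". Neither section gives the minimisation settings (cut-points, weights, assignment probability).

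Section 8.1 compares SCI between arms from baseline to immediately post-intervention, "following an intention to treat analysis approach". The default test is ANOVA, "or linear mixed model or non-parametric equivalents if necessary) with inclusion of baseline score as a covariate". In effect this is ANCOVA on baseline SCI. Age appears in no analysis model.

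For the remaining outcomes the text is shorter: "Secondary outcomes will be assessed with ANOVA (or linear mixed model or non-parametric equivalents if necessary"). No covariate is named there. Yet Section 5.5 collects the GAD-7, PHQ-9, Stroke Impact Scale-8, EQ-5D-5L, actigraphy and a sleep diary at baseline.

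Section 8.1 does not say what makes an alternative necessary, which mixed model or rank procedure is meant, or when the choice is made.

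**The concern.** Minimisation makes the arms more alike on age than chance would. If age predicts SCI, the treatment estimate then varies less from trial to trial than a model without age assumes. That model leaves the age-related variation in the residual, so it reports a standard error that is too large, a confidence interval that is too wide and a p-value that is too big on average. The design secures some precision that the analysis then does not use.

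For secondary outcomes, leaving out the outcome's own baseline value can lose more, because a patient's baseline is usually a stronger predictor than age.

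A separate matter is that three types of method are open for one primary outcome with no rule for choosing between them. This could raise the false-positive rate if the choice were influenced by the results. The two matters act in opposite directions on type I error and should be kept apart.

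**Working it through.** **Inputs from the documents.** Two arms 1:1, 68 complete datasets, d = 0.7, alpha 0.05, power 80% (Section 8.2); minimisation on baseline SCI and age (Sections 3 and 5.4); baseline SCI as the only covariate (Section 8.1).

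**Assumptions not in the documents.** Baseline-outcome correlation r = 0.5 (range 0.3 to 0.7); age-outcome correlation g = 0 to 0.4, with age unrelated to baseline SCI; minimisation on dichotomised factors with assignment probability 0.8; 2,500 simulated trials per setting, so a type I error near 5% carries about ±0.9 points of simulation error.

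**Plan's own figure.** A two-sided two-sample t-test at d = 0.7 needs 34 per arm, 68 in total (power 81.2%). At d = 1.2 it needs 24 in total (power 80.2%). Both stated figures reproduce. Neither calculation takes credit for any covariate.

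**Omitting age.** With outcome variance 1, the residual variance is 1 − r² without age and 1 − r² − g² with age. The ratio of reported standard errors is √[(1 − r²)/(1 − r² − g²)]. At r = 0.5:

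| g | Formula | Simulated mean SE, without / with age | Ratio |
|---|---|---|---|
| 0 | 1.000 | 0.2101 / 0.2108 | 0.997 |
| 0.2 | √(0.75/0.71) = 1.028 | 0.2100 / 0.2048 | 1.025 |
| 0.3 | √(0.75/0.66) = 1.066 | 0.2099 / 0.1974 | 1.063 |
| 0.4 | √(0.75/0.59) = 1.127 | 0.2101 / 0.1866 | 1.126 |

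At r = 0.7 and g = 0.4 the simulated ratio is 0.1726/0.1435 = 1.20.

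**Type I error without age.** If minimisation balanced age perfectly, then at r = 0.5 and g = 0.4 the effective critical value would be 1.96 × 1.126 = 2.21, a two-sided error of about 2.7%. Minimising on halves balances age only partly. Simulated error at g = 0.4 is 3.2–4.1% across r = 0.3 to 0.7 and normal or skewed errors, and about 3% in a separate set of runs. With age in the model it is 4.1–5.8% across all settings, which is nominal within simulation error.

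**Power at r = 0.5, without → with age, for g = 0.2, 0.3, 0.4.**
- d = 0.7: 92→93%, 92→94%, 92→96%.
- d = 0.5: 64→67%, 65→69%, 66→75%.

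**Secondary outcomes.** If a change score is analysed with no covariate, its standard error relative to ANCOVA is √[2(1 − r)/(1 − r²)] = √[2/(1 + r)]. This is 1.24, 1.15 and 1.08 at r = 0.3, 0.5 and 0.7. If the post value alone is analysed, the ratio is 1/√(1 − r²), which is 1.05, 1.15 and 1.40.

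**Open choice of test** (minimised allocation, age not prognostic). Taking the smallest p-value among ANCOVA, a group-by-time test on change and a rank test gives 5.6–7.0% with a Mann-Whitney test on change, and 6.6–7.8% with rank ANCOVA. Other runs gave about 5.5–6%. When a Shapiro-Wilk test on residuals decides the switch, the rate is 1.6–5.3%. At g = 0.4, even the smallest of three p-values gives only about 4.0–5.8%.

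**The case against.** The strongest defence is that ANOVA with baseline SCI is a clear default, so the minimisation factor likely to matter most is already in the model. Age may add little once baseline SCI is included, and the documents give no age-outcome correlation. At the planned d = 0.7, power is about 92% even without age if r = 0.5, so the trial does not depend on the change. All of this stands. It limits the size of the point; it does not explain why a factor chosen for minimisation is left out of the analysis. The assumed g is also on the generous side: at r = 0.5, g = 0.4 means a correlation of 0.4/√0.75 = 0.46 with what baseline SCI leaves unexplained.

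On secondary outcomes, Section 8.1 is silent on a covariate and does not exclude one, and the synopsis defines these outcomes as changes, so baseline values do enter. That stands too, but a change score without a covariate is still less precise than ANCOVA under the assumptions above.

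A reader might infer three stronger things that the documents do not support.
- *That the open choice of test gives a type I error of roughly 8–11%, or 14.3% as for three independent tests.* The 8–11% arises under simple randomisation with the smallest p-value taken. This trial is minimised, and the tests are highly correlated. The if-necessary clause also reads more naturally as a response to failed assumptions than to results.
- *That a rank test would discard the baseline adjustment for the primary outcome.* The covariate phrase follows the bracket and can govern all three options. Rank ANCOVA takes a covariate, and a mixed model with one post-baseline time point and baseline as covariate essentially reduces to ANCOVA.
- *That omitting age raises false positives.* It lowers them.

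**Conclusion.** The point holds as a free improvement. The primary analysis leaves out a minimisation factor, and the secondary analyses name no baseline covariate. With 68 participants and r = 0.5, omitting age makes the reported standard error about 3%, 6% and 12–13% too large at age-outcome correlations of 0.2, 0.3 and 0.4, rising to about 20% at r = 0.7 with 0.4. The loss is nil if age is not prognostic. The consequence is a conservative test and an interval that is too wide, not a spurious positive result. All of these sizes rest on correlations and minimisation settings that the documents do not give.

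The missing switching rule is mainly missing detail. Its worst case is a type I error of about 5.5–8% if the method is picked on results; a switch driven by a residual check brings no inflation.

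**What to change.** In Section 8.1:

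1. Name one primary model: post-intervention SCI on arm, with baseline SCI and age as continuous covariates.
2. Use the same model for each secondary outcome, replacing baseline SCI with that outcome's own baseline value where it is collected.
3. Label rank-based or other alternatives as sensitivity analyses, fixed before unblinding.

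This takes two or three sentences and needs no new data, since age and the baseline measures are already recorded under Section 5.5. It costs one degree of freedom for age (in simulation the standard error rises from 0.2101 to 0.2108 when age is irrelevant) and some freedom to change method after seeing the data.
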